### **7.3 Quantitative secondary distribution cohort data**

For the quantitative data arising from the secondary distribution cohorts, we will conduct analyses separately for the ANC and HIV testing and treatment cohorts. We will use descriptive analyses to describe the proportion of individuals accepting an offer of HIVST and the proportion who report that their partner used the HIVST. We will use standard logistic regression adjusting for study site to explore factors associated with accepting an offer of HIVST and with reported use of the HIVST.

Although the index individuals will be asked about linkage to care at 1-month follow-up, we will measure linkage to care using data from the intended users followed-up within 3-months after distribution. Linkage will be measured as the number of individuals reported to have linked to care (defined as accessing confirmatory testing services or attending an HIV care clinic for HIV-positive individuals or accessing VMMC services for HIV-negative males) among those who reported use of the HIVST.

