### **7.4 Cost data**

Cost data will be analysed separately by the economics team in STATA 14. Costs will be descriptively categorised into direct and indirect costs. To assess the economic burden HIVST,

we will compare sum of patients' direct non-medical and indirect costs with the household per capita expenditure. We will use a multivariable Tobit regression model to determine cost predictors.

Among individuals participating in the follow-up survey, we will describe reported use of the HIVST and investigate factors associated with reporting use of the secondary distribution HIVST. We will also describe linkage to ART or voluntary medical male circumcision, and time to linkage to care. Linkage data will primarily rely on reported use by the index individual, but we also aim to describe this among the intended users if consent is provided to follow-up partners and partners consent to participate in the study.

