Use_HIVST 3	Did you give your partner an HIV self-test kit that you collected on his behalf?	No; Yes	0; 1
Use_HIVST 3a	If no, why did you not give the HIVST to your partner?	I lost the kit; my partner already knows his/her HIV positive status; I feared my partner would get angry; my partner has been away from the time I collected the test kit; my partner and I are no longer in partnership; other (Specify); refuse to respond	1; 2; 3; 4; 5; 6; 7
Use_HIVST 4	Did your partner use the HIV self-test that you gave him?	Yes – I was present when he used the self-test; Yes – I was told that the self-test kit was used; No- he did not use the self-test kit; I Don't know	1; 2; 3; 4
Use_HIVST 5	What was the date that your partner used	Year; month; day	

	the HIV self-test kit?		
Use_HIVST 6	When your partner used the self-test, did you also use a self-test at the same time?	Yes (Couple testing); No; Don't know	1; 2; 3
Use_HIVST 7	What were the results of your self-test?	HIV-positive; HIV-negative; Indeterminate; Don't know; Refused to answer	1; 2; 3; 4; 5; 6
Use_HIVST 8	Do you know the results of your partner's HIV test?	No; Yes; Don't know; Refused to answer	1; 2; 3; 5
Use_HIVST 9	What was your partner's test result?  Interviewer: Remind participant that they do not have to answer this question if uncomfortable. If she says that she knows but doesn't want to share – this is code 99. If the person tested but did not share the result with them so they don't know, this is code 98	HIV-positive; HIV-negative; Indeterminate; Don't know; Refused to answer	1; 2; 3; 4; 5
Use_HIVST 10	Did your partner go to a clinic or health facility in order to confirm the result that was obtained from the self-test (confirmatory testing)?	No; Yes; Don't know	0; 1; 2
Use_HIVST 11	Did your partner go to a clinic or health facility for HIV care?	No; Yes; Don't know	0; 1; 2
Use_HIVST 122	Is your partner currently in ART care?	No; Yes; Don't know	0; 1; 2
Use_HIVST 13	Did your partner go to the clinic or health facility for HIV prevention services?	No; Yes; Don't know	0; 1; 2
Use_HIVST 14	What HIV prevention services did they go for?	VMMC; to collect condoms; other (specify)	0; 1; 2

Social Harms/benefits Screening at follow-up visit			
Variable Name	Question	Options	Option Codes

SHS_Fu_1	When you gave your partner the HIV test kits, did you explain that it is for HIV testing?	Yes; No; Don't know	1; 2; 3

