Drugs_2	In the last 12 months, have you used drugs recreationally?	No; Yes	0; 1
Drugs_3	In the last 12 months, which drugs have you used?	Cannabis/Marijuana; Cocaine/Crack; Khat/Miraa; Ecstasy/Disco biscuit; Heroin; Amphetamine/Speeed; Tik; Nyamba (any)	; 2; 3; 4; 5; 6; 7

		drug mixed with ART and smoked); Glue/solvents/petrol sniffing; Other (Specify)	
Section 6: Linkage to HIV care (Only for those who self-test HIV positive)			
Link_HIV_Care 1	After self-testing HIV positive, did you go to the clinic to confirm your results?	No; Yes	0; 1
Link_HIV_Care 2	What was result of your confirmatory test?	Negative; Positive; I don't know; Refuse to respond	1; 2; 3; 4
Link_HIV_Care 3	After confirming your HIV-positive status, did you register at the clinic for HIV services?	No; Yes	0; 1
Link_HIV_Care 4	If yes, what date did you register for HIV care?	MMYYYY	[01011900 if UNKNOWN]
Link_HIV_Care 5	At which clinic did you register for ART care?	At the clinic in my community; At another clinic outside my community; at a private clinic	1; 2; 3
Link_HIV_Care 6	At the clinic, were you given the result of a CD4 cell count test?	No; Yes; Don't know/Refused	0;1; -1
Link_HIV_Care 7	If yes, do you know the result of your last CD4 cell count test?	No; Yes	0; 1
Link_HIV_Care 8	What was the CD4 count result?		
Link_HIV_Care 9	Why did you not register at a clinic for HIV care?	Not ready; clinic too far from home;	1; 2; 3
Link_HIV_Care 10	Have you started taking ART treatment?	No; Yes	0; 1

Link_HIV_Care 11	When did you start taking ART?	DDMMYYYY	
Link_HIV_Care 12	Do you know people who are taking ART?	No; Yes	0; 1
Link_HIV_Care 8 1	Who was it you knew, who had been on ART? Please choose all that apply from:	Sexual partner; Household member(s) (not including sexual partner); friend(s)/neighbour(s)/colleague(s); other	1; 2; 3; 4
Link_HIV_Care 9	Have you disclosed your HIV status to anyone, except to me for the purpose of this study?	No; Yes	0; 1 If No skip to Link_HIV_Care 5
Link_HIV_Care 10	To whom did you disclose your HIV status?	husband/wife /Sexual partner; Family Member; Friend/neighbour/colleague; Religious leader/; Health care; Other	1; 2; 3; 4; 5
Link_HIV_Care 11	What are the reasons why you did not register for ART care?	The clinic is too far; The hours of the clinic don't suit me; I did not have transport to go the clinic; I'm not interested in ART	1; 2; 3; 4;

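### Time to linkage to care is a planned result, but the follow-up forms lack the dates it needs for most of the protocol's linkage definition; only time to ART start can be computed to the day

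*Protocol*

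**What the plan says.** Section 7.4 of the Protocol commits to the result: "We will also describe linkage to ART or voluntary medical male circumcision, and time to linkage to care". It also names a main informant: "Linkage data will primarily rely on reported use by the index individual", with intended users described where they consent.

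Section 7.3 names the other informant. It acknowledges that index individuals will be asked at one month, then states that "we will measure linkage to care using data from the intended users followed-up within 3-months after distribution". It gives the only definition of linkage, "defined as accessing confirmatory testing services or attending an HIV care clinic for HIV-positive individuals or accessing VMMC services for HIV-negative males".

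The questions are in Appendix 3:

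- **Index follow-up form.** The start of the interval is asked to the day (Use_HIVST 5, which begins "What was the date that your partner used"). Confirmatory testing, care ("Did your partner go to a clinic or health facility for HIV care"), current ART and prevention services each take no, yes or don't know. The last item, Use_HIVST 14, asks only which prevention service.
- **Intended-user form.** Kit use is asked as year, month and day. Confirmatory testing ("After self-testing HIV positive, did you go to the clinic to confirm your results") is yes or no, followed by the result. Care registration ("If yes, what date did you register for HIV care") is answered as MMYYYY, ART start as DDMMYYYY, and circumcision date as MM/YYYY.

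A note at the head of Appendix 3 says that response options, order and skip patterns may change when the devices are programmed.

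**The concern.** A time-to-event description needs a dated start and a dated end for each person. The start is recorded. For most of the events that count as linkage, the end is never asked, or is asked only to the month. A later analysis plan cannot repair this, because a date not asked at interview can be recovered only by contacting people again. At stake is whether the time-to-linkage sentence in section 7.4 can be delivered for the linkage that section 7.3 defines, or only for the subset of partners who start ART.

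**Working it through.** No figure in the protocol has to be reproduced. The check sets each linkage event against the questions that could date it.

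| Event | Index follow-up form | Intended-user form | Time to event |
|---|---|---|---|
| Confirmatory test (7.3) | Use_HIVST 10, no date | Link_HIV_Care 1 and 2, yes/no and result, no date | Not from either form |
| HIV care clinic (7.3) | Use_HIVST 11, no date | Link_HIV_Care 3 and 4, registration as MMYYYY | Intended user, to the month |
| VMMC, HIV-negative males (7.3) | Use_HIVST 13 and 14, no date | No date after the self-test (see below) | Not from either form |
| ART start (named in 7.4, not in the 7.3 definition) | Current ART only, no date | DDMMYYYY | Intended user, to the day |

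**VMMC skip.** Link_HIV_Care 15 offers three answers: no because already circumcised, no, and yes. The printed routing sends the second and third answers to Link_HIV_Care 19, past the circumcision date. Only men already circumcised reach the MM/YYYY item. The items from 19 onward ask about attendance, reasons, the decision and the place, but not when. A man who goes for VMMC after his self-test is therefore never asked for a date.

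**Uncertainty from month-only registration.** Section 7.4 names no time origin, so I take kit use, known to the day. If registration is known only by calendar month, the interval lies between

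- lower bound = max(0, first day of month − kit-use date), and
- upper bound = last day of month − kit-use date.

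The width is at most 31 − 1 = 30 days, and 30/90 = one third of a three-month window. For illustration, take a kit used on 10 August. Registration recorded as September gives 22 to 51 days, a width of 29. Registration recorded as August gives 0 to 21 days, a width of 21.

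The typical width depends on how quickly people register, which the protocol does not say. Simulated under assumed lags, with exponential lags truncated at 90 days:

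| Assumed lag from kit use to registration | Mean width | Registration month straddles day 90 |
|---|---|---|
| Exponential, mean 7 days | 19.6 days | about 0% |
| Exponential, mean 14 days | 22.4 days | 0.4% |
| Exponential, mean 30 days | 25.1 days | 3.4% |
| Uniform, 0 to 90 days | 27.7 days | 15.7% |

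With mid-month imputation over a full 30-day month, the largest error is about 15 days and the standard deviation is 30/√12 = 8.7 days. It is smaller when the kit-use date or the time-stamped interview date cuts the month short.

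**Undated yes answers.** These are not empty. The event lies between kit use and the interview, about one month after distribution for the index and about three months for the intended user. That bounds the time but does not measure it.

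**The case against.** The case for leaving the plan alone has four parts.

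- **The forms are provisional.** Month-and-year could become a full date, and the VMMC skip could be rewritten. The code for an unknown registration date, 01011900, already has eight digits, which suggests the format is unsettled. This stands for the registration format and the routing. It does not reach questions that do not exist: the Appendix 3 note covers response options, order and skips, not new items.
- **Time to ART start is available to the day** for consenting partners. This stands in full. A reader might infer that no time to linkage can be computed at all; the intended-user form contradicts that. But ART start is not in the section 7.3 definition, and it leaves out people whose only linkage is a confirmatory test or VMMC.
- **Section 7.3 makes the intended user the source,** so undated index items may matter little. Section 7.4 says the reverse, and the protocol does not settle it. A reader who takes section 7.4 alone might conclude that the main source is certain to fail; section 7.3 prevents that. Under either section, confirmatory testing and later VMMC remain undated.
- **The result is minor.** This stands. Time to linkage appears once, as description. The outcomes in section 4.3.2 are proportions, and section 5.4 says the linkage results are descriptive and that the study is not powered for factors associated with linkage. Asking index patients to date a partner's clinic visits could also yield guesses.

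The self-referral card in Appendix 6 carries an ART enrolment date, but nothing in the protocol makes it a source for the cohort analysis.

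**Conclusion.** The point holds, with limited reach. Of the three components of linkage in section 7.3, confirmatory testing and VMMC after the self-test are undated in both forms, and care attendance is dated only to the month, by intended users. Time to ART start is the one interval available to the day. The index form dates no linkage event.

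The size rests on two assumptions. One is that the printed month-and-year format and the VMMC skip are kept. The other is that kit use is the time origin. Two stronger readings should be avoided. Thirty days is the upper limit of the uncertainty window, not a typical error; mean widths ran from about 20 to 28 days under the assumed lags. And the circumcision item should not be read as a month-level date for linkage, because the printed routing reserves it for men already circumcised.

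The primary outcome and the sample size are unaffected. The loss is confined to a secondary, descriptive result, but it cannot be made good once interviews are done.

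**What to change.** Before the devices are programmed:

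1. In the intended-user form, add a date for the confirmatory test and for VMMC attended after the self-test, with a best guess allowed as for kit use. Record care registration as DDMMYYYY.
2. Reconcile sections 7.3 and 7.4 on whether the index or the intended user is the source for linkage. If index reports are kept for time to linkage, add a date to each yes at Use_HIVST 10, 11 and 13. Otherwise state that time to linkage comes from intended users only.
3. If the dates are not added, restrict the section 7.4 result to time to ART start.

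The cost is a few extra recall items per interview, with some recall error in the answers. No sample-size or power figure changes.

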## **Appendix 4. Qualitative Interview Guides and Observation form**

### **Qualitative-Cohort: In-depth Interview for Index partner (first interview)**

Thank you for taking time to speak with me today. My name is \_\_\_\_\_ and I am working with Zambart a research organization. In order to increase the uptake of HIV services, HIV self – testing kits are being distributed at the ARTs clinic and ANC. We would like to hear what you think about this as well as what the community thinks. We will record the interview in order to make sure that we capture all of the valuable information that you share with me. We will also be taking down notes so that I do not forget what we have discussed. Please feel free to give honest answers as what we say is confidential. We will not record your name on the tape or on the notes that will be written and no one else will see the tape or the notes besides people who are working on this research project.

#### **A. General information**

1. (record sex of participant):
2. What year were you born?
3. Where do you live- zone/ section of the community?
4. What is your marital status?
5. How far did you go in your education?
6. What do you do for a living? What does your partner do for a living?
7. What is your religion?

#### **B. Knowledge of HIV/ HIVST and attitudes towards testing for HIV?**

1. Have you ever tested for HIV before? What methods did you use to test? What are the advantages and disadvantages of testing for HIV using this/ these method (s)?
1. How often do you test for HIV and why? It usually takes a long time/ a short time before you test, why? (Probing for attitudes). What about your partner, how often do they test?
2. How often do you come to access HIV services here and why? Have you ever come to access testing services from here with your partner? If so why, if not why

#### **C. Community factors and stigma**

1. What other testing services are available in this community?
2. How did the availability of other testing services other than HIVST affect your decision?
3. How did your anticipation of what people may say after you have tested using HIVST influence your decision? What do you expect people to say?
4. How did having these friends and family members influence your decision to accept/ decline of HIVST?
5. You were told about the advantages and disadvantages of HIVST? How did these apply to your situation? (Probe).

**D. Knowledge of and experiences with secondary distribution of HIVST Kit**

1. What do you think about HIVST?
2. How does it work or not work for you- in your situation? ( probe for advantages and disadvantages)
3. You decided to accept/ decline offer of HIVST kit that you delivered to your partner, was there any reason why?
4. Before getting the test kit, did you ask for permission from your partner? If so, how did you do it? What was his response,
5. If he said yes, what was the reason behind him agreeing?
6. If he said no, did you go ahead to get him a test kit? Why did you do so?
7. How did your partner react to the fact that you accepted HIVST without consulting him/her? (describe in detail how your partner will react to the news that you have accepted HIVST- support, anger, will not care, violence)

**E. Distribution of test kits**

1. Why did you decide to come and collect the test kit from this distribution point?
2. What did you like about the location of this distribution point? (probe: distance from home, No stigma,)
3. What is it that you didn't like about the location of this distribution point? (probe: distance from home, stigma, being located within the clinic)
4. How did the location (within the clinic or within the community) improve or hinder your access of HIVST services? (probe)
5. How did the location (within the clinic or within the community) influence your decision to accept or reject HIVST? (probe)

Can you explain to me the how you managed to get the test kit? (Who and how it you ask for it, what were you told about the test?)

**F. Role of HCWs**

1. How did the characteristics of person (man, woman, age) who distributed the HIVST influence your decision?
2. In your opinion is it alright for SFH staff/ HCWs to be distributing HIVST at this distribution point? What are the advantages and disadvantages?

## **G. Home environment (including Power and social relations)**

1. When you reached home, how did you offer the test kit your partner? (Probe on the time of offer, what information was given out and the response)
2. You accepted/ rejected offer of HIVST. How did your relationship with your partner influence your decision?
3. Did your partner test after you offered him the test kit and explained how the test was to be done? How easy was it for you to explain to him how to use the kit? Did you face any challenges, what was easy/difficult to explain? What about him, how did he find the testing process? Was it easy or difficult to test following instructions from you? Was there anything else that helped him with the testing( IFU, pictures on the IFU, your demonstrations)
4. Where did your partner test from? (Was it in your presence, alone, did he share results with you? Did you test as a couple)?
5. If your partner refused to test, was there any reason given? What do you think can make them test in the future?
6. Were there any beliefs that influenced your decision? What beliefs/ issues influenced your decision?

## **H. Social harms**

1. After delivering the test kit to your partner, did you experience any problems?
2. Please describe any kind of problems you faced? For example: beaten, yelled at, denied sex, marriage break-up, not given money, being locked out, being neglected, or being threatened.
3. What do you think made your partner respond to you in such a way?

What is it that you think we can do to prevent such problems from happening again in the future (probe: can home based counselling work,

## **I. Linkage to care:**

1. After testing, did your partner share with you his results?
2. What was his next step after knowing his results?
3. **If the partner shared the results:** What advise did you give him concerning his results (probe on linkage to care if the participants shared the HIV positive results or on linkage to MMC for negative ones)
4. **If the results were positive:** did you advise him on getting linked to ART? What was his response? If he agreed, why did he do so? If not, why did he not want to get linked? If he got linked, how long did it take him to get up and go to the clinic? Did you go with him? What was the experiences of getting linked at the facility, where were any challenges that he or both of you faced? (Probe: was stigma a problem for you or for him, what about congestion?)

**If the results were negative,** did you encourage him about getting linked to MMC? What was his response? If he agreed, why did he do so? If not, why did he not want to get linked?

**J. Promotion and social marketing**

1. Had you heard about HIVST before today? Where did you hear it from?
2. Did having this information about HIVST before today influence your decision to accept or not to accept HIVST today?
3. How was this information presented to you/ community? In what ways can presentation (sensitization about) of HIVST information be done better in a community like yours and people like you

We have come to the end of the interview. Thank you

### **Qualitative-Cohort: In-depth Interview for Primary partner (first interview)**

Thank you for taking time to speak with me today. My name is \_\_\_\_\_ and I am working with Zambart a research organization. In order to increase the uptake of HIV services, HIV self – testing kits are being distributed at the ARTs clinic and ANC. We would like to hear what you think about this as well as what the community thinks. We will record the interview in order to make sure that we capture all of the valuable information that you share with me. We will also be taking down notes so that I do not forget what we have discussed. Please feel free to give honest answers as what we say is confidential. We will not record your name on the tape or on the notes that will be written and no one else will see the tape or the notes besides people who are working on this research project.

#### **A. General information**

1. (record sex of participant):
2. What year were you born?
3. Where do you live- zone/ section of the community?
4. What is your relationship with the person who gave you the test kit? Wife, living together?
5. How far did you go in your education?
6. What do you do for a living? What does your partner do for a living?
7. What is your religion?

